1.1. Synopsis

Protocol Title: A 6-Month Extension Study Following Protocol VMDN-003-2 – An Adaptive, Phase 3, Double-Blind, Randomized, Placebo-Controlled, Multicenter Study to Assess the Safety and Efficacy of Engensis in Participants with Painful Diabetic Peripheral Neuropathy

Short Title: A 6-Month Phase 3 Extension of a Study to Assess Safety and Efficacy of Engensis in Painful Diabetic Peripheral Neuropathy

Rationale:

The purpose of this 6-month extension study (VMDN-003-2b) is to evaluate the durability of efficacy and long-term safety of intramuscular (IM) administration of Engensis or Placebo that was administered in the double-blind, randomized, VMDN-003-2 Placebo-controlled Phase 3 Study. No treatments will be administered in this VMDN-003-2b extension study. The combined overall duration of the VMDN-003-2 and VMDN-003-2b studies will be 12 months.

Engensis contains the active pharmaceutical ingredient VM202, a novel genomic complementary deoxyribonucleic acid (cDNA) hybrid human hepatocyte growth factor (HGF) coding sequence (HGF-X7) expressing two isoforms of HGF, HGF₇₂₈ and HGF₇₂₃, being developed for treatment of painful DPN.

In the VMDN-003-2 main study, Participants will have received Engensis or Placebo by IM injections in both legs (in the calf gastrocnemius muscles) during two Treatment Cycles (Treatment Cycle 1 on Days 0 and 14 and Treatment Cycle 2 on Days 90 and 104).

Data from Study VMDN-003-2 assessments at or prior to the Day 0, Day 104, and Day 180 Visits for Participants who enroll in Study VMDN-003-2b will be used as reference points for changes in efficacy parameters and for safety assessments during this extension study.

Objectives and Endpoints

Objectives	Endpoints
Primary	
To evaluate the efficacy of IM administration of Engensis on pain in participants with painful DPN in the feet and lower legs as compared to Placebo	Change in the means of the Average Daily Pain Scores (ADPSs) from the full Brief Pain Inventory for Diabetic Peripheral Neuropathy (BPI-DPN) from the 7 days prior to the Day 0 Visit (Study VMDN-003-2) to the 7 days prior to the Day 365 Visit in the intent-to-treat (ITT) population

Version 1.0 8 Final: 11 Feb 2021

Objectives	Endpoints
Secondary Efficacy:	
To evaluate the efficacy of IM administration of Engensis on the worst pain in Participants with painful DPN in the feet and lower legs as compared to Placebo	Change in the means of the Worst Pain scores from the full BPI-DPN from the 7 days prior to the Day 0 Visit (Study VMDN-003-2) to the 7 days prior to the Day 270 Visit and the 7 days prior to the Day 365 Visit for Engensis compared to Placebo
To evaluate the efficacy of IM administration of Engensis on reducing pain in Participants with painful DPN in the feet and lower legs as compared to Placebo	 Proportion of Responders (≥ 50% reduction in the ADPSs from the full BPI-DPN) from the 7 days prior to the Day 0 Visit (Study VMDN-003-2) to the 7 days prior to the Day 270 Visit and the 7 days prior to the Day 365 Visit for Engensis compared to Placebo
Secondary Safety:	
To evaluate the safety of IM administration of Engensis in Participants with painful DPN in the feet and lower legs as compared to	◆ Incidence of treatment-emergent adverse events (TEAEs) and treatment-emergent serious adverse events (TESAEs) for Engensis compared to Placebo
Placebo	Incidence of clinically significant laboratory values for Engensis compared to Placebo

Version 1.0 Final: 11 Feb 2021

Overall Design

VMDN-003-2b is a 6-month extension study following Study VMDN-003-2, which is an adaptive, Phase 3, double-blind, randomized, placebo-controlled, multicenter study designed to assess the efficacy and safety of Engensis (containing the active pharmaceutical ingredient VM202) in Participants with painful DPN.

The purpose of this study is to assess the durability of efficacy and long-term safety of Engensis compared to Placebo as measured by changes in Average Daily Pain Score (ADPS) of the full Brief Pain Inventory for Diabetic Peripheral Neuropathy (BPI-DPN), Bedside Sensory Testing (BST), physical examinations, laboratory assessments, vital signs, treatment-emergent adverse events (TEAEs), treatment-emergent serious adverse events (TESAEs), and adverse events of special interest (AESIs).

Participants will be enrolled in the VMDN-003-2b study at completion of the Day 180 Visit of Study VMDN-003-2. Participants will continue to be identified by the same Participant number and the same treatment group (Engensis or Placebo) assigned by randomization in Study VMDN-003-2. No study drug or treatment will be administered in this VMDN-003-2b extension study. The double-blind treatment assignment from the prior study will be maintained for Investigators and Participants during this extension study.

Assessments to be conducted during this VMDN-003-2b extension study are as follows: vital signs, weight, BMI, physical examination, retinal fundoscopy (by an ophthalmologist), 12-lead electrocardiogram (ECG), laboratory assessments, HBA1c levels, concomitant medications and procedures, urine drug analysis, urine pregnancy test for females of childbearing potential, Accurate Pain Reporting (APR), Placebo Response Reduction (PRR), the Michigan Neuropathy Screening Instrument (MNSI), partial and full BPI-DPN, BST, and quality of life instruments (36-item Short Form Health Survey [SF-36] and EuroQol Health Utilities Index [EQ-5D]).

Assessments of TEAEs, TESAEs, AESIs, and clinically significant laboratory values will start as of the Day 180 Visit of Study VMDN-003-2 and continue throughout the VMDN-003-2b extension study through Day 365/ET.

During the last 7 days prior to the Day 270 and Day 365/ET Visits, Participants must complete the full BPI-DPN on an ePRO for determining the ADPS for at least 5 out of the last 7 days.

Follow-up Study Visits will be conducted on Days 270, 300, and 365/ET. At the Day 365/ET Visit (end of study), the following assessments will be conducted: the full BPI-DPN (performed during the 7 days prior to the Visit), MNSI, BST, Patient Global Impression of Change (PGIC), SF-36 and EQ-5D quality of life assessments, urine drug analysis, retinal fundoscopy, physical examination, concomitant medications and procedures, TEAEs, and AESIs. Blood will be drawn for determination of serum chemistry, lipid profile, pregnancy status, hematology, and HbA1c levels.

Version 1.0 11 Final: 11 Feb 2021

Study and Treatment Duration:

The timing for visits in the VMDN-003-2b study starts at the conclusion of the Day 180 Visit in Study VMDN-003-2. Participants in Study VMDN-003-2b will be followed from the Day 180 Visit (VMDN-003-2) to Day 365/ET. The VMDN-003-2b study duration is 6 months.

No study drug or treatment will be administered in Study VMDN-003-2b.

Visit Frequency:

There will be 3 visits to the Clinical Site during the extension study (after the Day 180 Visit from Study VMDN-003-2) on Days 270, 300, and 365/ET.

Intervention Groups and Duration:

Two treatment groups of Participants (Engensis or Placebo) from Study VMDN-003-2 will be followed in a double-blind fashion from Day 180 Visit (Study VMDN-003-2) through Day 365/ET of this extension protocol. No study drug (Engensis or Placebo) will be administered in the VMDN-003-2b study.

Number of Participants:

[figure not shown]
The number of Participants to be enrolled in this 6-month extension study depends upon the number of subjects who complete the Day 180 Visit in Study VMDN-003-2 and provide written informed consent for this extension protocol (prior to or during their Day 180 Visit in the VMDN-003-2 study).

Data Safety Monitoring Board:

The independent Data Safety Monitoring Board (DSMB) will periodically review a limited set of unblinded (noncomparative) tables and/or listings, including all reported TEAEs, TESAEs, and AESIs.

Version 1.0 12 Final: 11 Feb 2021

1.2. Study Schema

Version 1.0 13 Final: 11 Feb 2021

1.3. Schedule of Activities (SoA)

		Follow-	up Visits	End of Study/ET
Study Days ^a :		Day 270	Day 300	Day 365/ET
	Visit Window (days):	± 7	± 7	± 7
	d Consent (obtained prior to or during the Participant's Day 180 Study VMDN-003-2)			
1	Vital Signs, Weight	X	X	X
2	Complete Physical Examination	X	X	X
3	Retinal Fundoscopy	X		X
4	12-Lead Electrocardiogram	X		X
5	Serum Chemistry, Hematology, Lipid Profile	X		X
6	Urine Pregnancy Test			X
7	Urine Drug Analysis	X	X	X
8	HbA1c Levels			X
9	Concomitant Medications and Procedures	X	X	X
10	Accurate Pain Reporting (APR), Placebo Response Reduction (PRR)	X	X	X
11	Full Brief Pain Inventory-Diabetic Peripheral Neuropathy (BPI-DPN)	X		X
12	Partial BPI-DPN (ePRO)	•		
13	Quality of Life (SF-36, EQ-5D)	X		X
14	Patient Global Impression of Change (PGIC)	X		X
	Treatment-emergent Adverse Events (TEAEs)	4		
15	Treatment-emergent Serious Adverse Events (TESAEs)	4		
	Adverse Events of Special Interest (AESIs)	4		
16	Michigan Neuropathy Screening Instrument (MNSI)	X		X
17	Bedside Sensory Testing (BST)	X		X

FOOTNOTES FOR SCHEDULE OF ACTIVITIES

*Schedule of Activities includes activities during Screening and all Study Visits. Additional data from daily ePRO entries will be transferred directly into a study database.

Abbreviations: AESI = adverse event of special interest; APR = Accurate Pain Reporting; BMI = Body Mass Index; BPI = Brief Pain Inventory; BST = Bedside Sensory Testing; D = Day; DPN = diabetic peripheral neuropathy; ePRO = electronic diary; ET = Early Termination; EQ-5D = EuroQol Health Utilities Index; HbA1c = hemoglobin A1c; MNSI = Michigan Neuropathy Screening Instrument (MNSI); PGIC = Patient Global Impression of Change; PRR = Placebo Response Reduction; SF-36 = 36-Item Short Form Health Survey; TEAE = treatment-emergent adverse event; TESAE = treatment-emergent serious adverse event

- Study days for this extension protocol are based on the time (in days) from Day 0 in Study VMDN-003-2.
- 1. Vital Signs and Weight: Vital signs and weight will be measured on Days 270, 300, and 365/ET. After the Participant has rested in the seated position for 5 minutes, vital signs will be collected, including temperature, sitting blood pressure, heart rate, respiratory rate, and oxygen saturation on room air. The method of

Version 1.0 14 Final: 11 Feb 2021

temperature measurement should be according to the Site's policy and should be consistently applied.

- 2. Complete Physical Examinations will be performed on Days 270, 300, and 365/ET. The examination will include the following: head, eyes, ears, nose, and throat (HEENT); heart; lungs; abdomen; extremities; lymph nodes; neurological; and skin/integumentary systems. Any abnormalities should be categorized as clinically significant (CS) or not clinically significant (NCS), and the abnormalities should be recorded as adverse events using appropriate medical terminology.
- 3. **Retinal Fundoscopy** will be performed by an ophthalmologist up to 30 days before the Day 270 and 365 Visits (and, if possible, upon Early Termination if the Participant discontinues prior to the Day 365 Visit). Results of the fundoscopy examinations at the Day 270 and Day 365 Visits compared to results at the Day 180 Visit (Study VMDN-003-2) will be assessed by the Investigator.
- 4. 12-Lead Electrocardiogram (ECG) will be performed on Days 270 and 365/ET. The ECG recording and interpretation will be printed out and stored with the Participant's records. Any newly identified abnormalities are to be recorded as adverse events.
- 5. **Serum Chemistry, Hematology, and Lipid Profile:** These laboratory assessments will be evaluated on Days 270 and 365/ET.
 - Chemistry includes sodium, potassium, chloride, bicarbonate, calcium, inorganic phosphate, magnesium, glucose, amylase, lipase, creatine kinase, lactate dehydrogenase, and
 - o Kidney function tests (blood urea nitrogen, creatinine)
 - Liver function tests (aspartate aminotransferase [AST], alanine aminotransferase [ALT], alkaline phosphatase, gamma-glutamyl transpeptidase [GGT], total bilirubin, total protein, and albumin)
 - Hematology includes platelet count, hemoglobin, hematocrit, white blood cell count, and neutrophil
 count
 - Lipid Profile includes total cholesterol, high-density lipoprotein cholesterol (HDL-C), low-density lipoprotein cholesterol (LDL-C), and triglycerides
- **6. Urine Pregnancy Test:** Pregnancy tests for women of childbearing potential will be conducted in the clinic on Day 365/ET.
- 7. Urine Drug Analysis includes amphetamines (methamphetamine), barbiturates, benzodiazepines, buprenorphine, cannabinoid (THC), cocaine, oxycodone, methadone, opiates, phencyclidine (PCP), tricyclics (TCA), and ethyl alcohol. Cannabinoid detection is not an exclusion criterion but may be used in exploratory analyses. The urine drug analyses will be conducted on Days 270, 300, and 365/ET. Drug analyses will be performed by the central laboratory.
- **8. HbA1c** levels will be measured on Day 365/ET.
- 9. Concomitant Medications and Procedures: All medications or vaccines, including over-the-counter or prescription medicines, vitamins, herbal supplements, and procedures that the Participant receives will be recorded on Days 270, 300, and 365/ET. For each medication, treatment, or procedure, the following information will be collected: Medication trade or generic name or type of procedure, indication, start date, stop date or ongoing, dose, units, frequency, and route.
- Accurate Pain Reporting (APR): The Accurate Pain Reporting training will be conducted on Days 270, 300, and 365/ET.
 - **Placebo Response Reduction (PRR):** The Placebo Response Reduction training will be conducted on Days 270, 300, and 365/ET.
- 11. Brief Pain Inventory (BPI-DPN) Full Questionnaire will be administered through the ePRO daily starting at 7 days prior to Day 270 and Day 365/ET. The mean of the Average Daily Pain Scores (ADPSs, used for the primary endpoint) is the mean from a minimum of 5 ADPSs recorded in the 7 days prior to the Days 270 and 365/ET Visits. If the ePRO contains fewer than 5 daily entries over the 7 days prior to the Day 270 and Day 365/ET Visits, the visit must be rescheduled (up to 3 days later) so that the Participant can record 5 daily entries over the 7 days.
- **12. Brief Pain Inventory (BPI) Partial Questionnaire** (questions 3, 5, and 9a from the full questionnaire) will be completed on the ePRO every day that the full BPI is *not* conducted from the Day 180 Visit (VMDN-003-2, Initial Visit for this extension study) to the Day 365/ET Visit.

Version 1.0 15 Final: 11 Feb 2021

- 13. Quality of Life Questionnaires (SF-36, EQ-5D) will be administered on Day 270 and Day 365/ET. The study coordinator will check the questionnaires for completeness. Any omissions or ambiguous answers will be clarified by the Participant prior to leaving the clinic.
- 14. Patient Global Impression of Change (PGIC) will be administered on Days 270 and 365/ET.
- 15. Treatment-emergent Adverse Events (TEAEs) will be monitored throughout the study and will be recorded after from the Day 180 Visit (VMDN-003-2) until Day 365/ET in this extension study. Any TEAEs that started during Study VMDN-003-2 and were ongoing at the Day 180 Visit will continue to be followed after Day 180 during this extension protocol. Adverse events that occur in this protocol will be referred to as TEAEs.

 Treatment-emergent Serious Adverse Events (TESAEs) will be recorded and reported to the Sponsor within 24 hours of awareness of the TESAE by the Site.
 - Adverse Events of Special Interest (AESIs): All AESIs will be continuously monitored throughout the study.
- **16. Michigan Neuropathy Screening Instrument (MNSI)** will be administered on Day 270 and Day 365/ET for assessing disease progression during the study.
- 17. **Bedside Sensory Testing (BST)** will be administered on Day 270 and Day 365/ET to provide additional information that will allow exploratory analysis of BST sensory profiles.

Version 1.0 Final: 11 Feb 2021

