8. STUDY ASSESSMENTS AND PROCEDURES

Study procedures and their timing are summarized in Section 1.3 (SoA).

Protocol waivers or exemptions are not allowed. Adherence to the protocol requirements, including those specified in the SoA, is essential.

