8.3. Safety Assessments

8.3.1. Physical Examinations

Complete physical examinations (PEs) will be performed at the Day 270, Day 300, and Day 365/ET Visits; and at the last Visit if the Participant discontinues prior to Day 365. The complete PE will include the following: an examination of the skin/integumentary systems, general appearance, head, neck (including thyroid), eyes, ears, nose, throat, lymph nodes, chest (lungs), heart, abdomen, musculoskeletal system, neurological system, and any additional assessments needed to establish baseline status or evaluate symptoms or TEAEs. Any physical examination abnormalities considered to be clinically significant (CS) should be added to TEAEs using medically appropriate terminology.

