8.3.2. Medical History and Familial History of Cancer

Medical history for this extension study will be based on the medical history information recorded at Screening for Study VMDN-003-2.

Medication history will be based on recorded medications within 30 days prior to the Day 180 Visit of Study VMDN-003-2.

Elevated risks of cancer for type 2 diabetes or obesity are detailed in Section 8.4.5, Adverse Events of Special Interest.

Version 1.0 39 Final: 11 Feb 2021

Helixmith Co., Ltd. CONFIDENTIAL VMDN-003-2b

8.3.3. 12-Lead Electrocardiograms

12-Lead electrocardiograms (ECGs) will be performed on Days 270 and 365/ET. Any clinically significant abnormalities are to be reported as adverse events. The ECG recording will be printed, and the investigator or delegated staff will initial and date the printout to indicate their review of the findings. The trace and the interpretation will then be stored with the Participant's records.

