10.2.1. Definition of AE

Note the definitions for AEs and SAEs presented below also apply to TEAEs and TESAEs in this protocol.

AE Definition

- An AE is any untoward medical occurrence associated with the use of an investigational product or study procedure in a clinical study Participant whether or not considered related to the study intervention.
- NOTE: An AE can therefore be any unfavorable and unintended sign (including an abnormal laboratory finding), symptom, or disease (new or exacerbated) temporally associated with the use of study intervention or procedure.

Events Meeting the AE Definition

- Any abnormal laboratory test results (hematology, or clinical chemistry) or other safety
 assessments (e.g., ECG, radiological scans, vital signs measurements), including those
 that worsen from baseline, considered clinically significant in the medical and
 scientific judgment of the investigator (i.e., not related to progression of underlying
 disease).
- Exacerbation of a chronic or intermittent pre-existing condition including either an increase in frequency and/or intensity of the condition.
- New conditions detected or diagnosed after study intervention administration even though it may have been present before the start of the study.
- Signs, symptoms, or the clinical sequelae of a suspected drug-drug interaction.
- Signs, symptoms, or the clinical sequelae of a suspected overdose of either study intervention or a concomitant medication. Overdose per se will not be reported as an AE/TESAE unless it is an intentional overdose taken with possible suicidal/selfharming intent. Such overdoses should be reported regardless of sequelae.

Events **NOT** Meeting the AE Definition

- Any clinically significant abnormal laboratory findings or other abnormal safety
 assessments that are associated with the underlying disease, unless judged by the
 Investigator to be more severe than expected for the Participant's condition.
- The disease/disorder being studied or expected progression, signs, or symptoms of the

Version 1.0 61 Final: 11 Feb 2021

disease/disorder being studied, unless more severe than expected for the Participant's condition.

- Medical or surgical procedure (e.g., endoscopy, appendectomy): the condition that leads to the procedure is the AE.
- Situations in which an untoward medical occurrence did not occur (social and/or convenience admission to a hospital).

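### The Schedule of Activities footnotes and sections 8.3.1, 8.3.3 and 10.2.1 give different rules for when an ECG or physical-examination finding becomes an adverse event, so new findings that are not clinically significant count as TEAEs at some sites and not at others

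*Protocol*

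**What the plan says.** **Physical examination.** SoA footnote 2 (protocol 1.3) first has the site sort abnormalities into CS and NCS. It then says that "the abnormalities should be recorded as adverse events using appropriate medical terminology". Section 8.3.1 is narrower: "Any physical examination abnormalities considered to be clinically significant (CS) should be added to TEAEs using medically appropriate terminology".

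**ECG.** SoA footnote 4 says: "Any newly identified abnormalities are to be recorded as adverse events". Section 8.3.3 says: "Any clinically significant abnormalities are to be reported as adverse events".

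**AE definition.** Appendix 2, section 10.2.1, counts abnormal laboratory results and other safety assessments (ECG is named) as AEs, including those "that worsen from baseline, considered clinically significant in the medical and" scientific view of the investigator. It excludes expected signs of the disease under study unless they are more severe than expected.

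**Status of the SoA.** Section 8 allows no waivers and states: "Adherence to the protocol requirements, including those specified in the SoA, is essential".

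**Route to the endpoint.** SoA footnote 15 adds: "Adverse events that occur in this protocol will be referred to as TEAEs". TEAE incidence is a secondary safety endpoint (protocol 3 and 9.3.2). SAP 12.6.1 restricts AE summaries to events starting after the Day 180 visit and to pre-existing conditions that worsen after it.

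**The concern.** A site reading the SoA and a site reading section 8.3 can see the same minor new finding, such as a new ECG change judged NCS, and treat it differently. One opens an AE record and the other does not. The SAP does not undo this, because its TEAE rule looks only at timing and worsening.

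What is at stake is the meaning of the TEAE rate. It would partly reflect which text each site followed. Findings of no clinical consequence would add background events to both arms and make any real arm difference in the overall TEAE rate look smaller. SAP 12.6.5 only lists ECG values, and SAP 12.6 has no physical-examination summary. During the extension, therefore, the AE tables are the only place where these findings are tabulated, and the recording rule decides what a reader sees.

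**Working it through.** The plan states no figure for this point, so there is nothing to reproduce. The check is a comparison of texts, followed by an illustration on assumed rates.

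**1. Which findings become AEs under each text**

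| Finding | SoA footnotes 2 and 4 | Sections 8.3.1 and 8.3.3 | 10.2.1 |
|---|---|---|---|
| New ECG abnormality, NCS | AE | not an AE | not an AE |
| New ECG abnormality, CS | AE | AE | AE |
| ECG abnormality, CS but not new | not covered | AE | AE if CS and not simply the underlying disease |
| New examination abnormality, NCS | AE if read literally | not an AE | not an AE |
| New examination abnormality, CS | AE | AE | AE |

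For ECG, neither rule contains the other. Footnote 4 tests novelty and not significance; 8.3.3 tests significance and not novelty.

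**2. What survives into the TEAE tables**

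- Unchanged earlier findings should drop out. Protocol 10.2.2 requires an event to be absent before treatment or to worsen, and SAP 12.6.1 requires onset or worsening after Day 180.
- Expected neuropathy signs should drop out under 8.4.9 and 10.2.1.
- New NCS findings recorded as AEs stay in, because SAP 12.6.1 has no test of clinical significance.
- One leak remains. SAP 12.6.1 counts an AE with no start date as a TEAE if its stop date is missing or falls after Day 180. An old finding of unknown onset, if entered as an AE, could pass that way.

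**3. Illustrative size**

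No document gives these rates; all are assumptions. Let p be the share of participants with a TEAE under the CS-only rule. Let q be the share with a new NCS finding, independent of p and equal in both arms.

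- Incidence when the footnotes are followed: p + (1 − p)q.
- Arm difference when the footnotes are followed: (p₁ − p₀)(1 − q).

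With p₁ = 40% and p₀ = 30%:

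- q = 5%: 0.40 + 0.60 × 0.05 = 43.0%, and 0.30 + 0.70 × 0.05 = 33.5%. Difference: 10 × 0.95 = 9.5 points.
- q = 30%: 0.40 + 0.60 × 0.30 = 58.0%, and 0.30 + 0.70 × 0.30 = 51.0%. Difference: 10 × 0.70 = 7 points.

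Two groups of sites with the same 40% rate under the CS-only rule would report 40% if they follow section 8.3, and 43% to 58% if they follow the footnotes. The gap of 3 to 18 points comes from the recording rule alone.

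These figures assume that every NCS finding is recorded at every site. If only some sites follow the footnotes, the study-wide shrinkage factor lies between (1 − q) and 1.

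**The case against.** - **Appendix 2 already governs.** Sections 8.4.1 and 8.4.3 send the reader there for TEAE definitions and recording, and section 8 describes the SoA as a summary of procedures. This is a good argument for how the conflict should be resolved. It is not a precedence clause, and the same section 8 makes SoA adherence essential.
- **Footnote 2 can be read as CS only.** It asks for CS/NCS sorting just before the recording instruction, and 8.3.1 suggests what the sorting is for. That stands: footnote 2 is ambiguous, and only its literal reading conflicts. The reading does not help footnote 4, which has no CS wording at all.
- **Impact is limited.** Safety is descriptive, with no formal testing (protocol 9.3.4, SAP 12.6). SAP 12.6.1 also tabulates TEAEs by preferred term, severity, relationship, seriousness and discontinuation, so dilution mainly affects the overall TEAE rate. This stands.
- **The case report form is not available here.** Version 3.0, cited in SAP 6.0, may decide whether an NCS entry opens an AE record. That could reduce the problem in practice but would not reconcile the protocol.

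A reader might also infer that nearly every participant would acquire a TEAE, because painful diabetic neuropathy usually brings an abnormal neurological or foot examination. The documents do not support this. Footnote 4 covers only new findings, and the provisions in step 2 of the working remove unchanged and expected ones, apart from the small leak for undated events.

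**Conclusion.** The inconsistency is real in the current text (Version 1.0, no amendments). It is clear for ECG and depends on a literal reading for the physical examination. It reaches a secondary safety endpoint through new NCS findings.

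Its size cannot be derived from the documents. On an assumed q of 5% to 30%, equal in both arms and independent of other TEAEs, a 10-point difference becomes 9.5 to 7 points. The lower figure needs the top of that range and full recording at every site.

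It would be wrong to infer bias toward one arm or a loss of power. Participants and sites are blinded, so the extra events should fall similarly in both arms, and no safety test is planned. The harm is to the level of the TEAE rate, its comparability between sites and, to a lesser degree, the visible contrast between arms. It is worth correcting, but it does not threaten the trial's conclusions on efficacy.

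**What to change.** 1. **Protocol.** Reconcile SoA footnotes 2 and 4 with 8.3.1, 8.3.3 and 10.2.1 so that one rule applies. Abnormalities judged clinically significant under the 10.2.1 definition are entered as AEs, and NCS findings stay on the examination or ECG form. Leave the new-or-worsened test to the TEAE definition (10.2.2, SAP 12.6.1). Adding it to the recording rule would create a narrower rule that neither 8.3.1 nor 8.3.3 contains.
2. **SAP 12.6.1.** State how NCS findings already entered as AEs are handled in the TEAE tables, and settle this before unblinding.
3. **SAP 12.6.** Add a simple by-arm table of CS and NCS findings for ECG and physical examination at each scheduled visit. SAP 12.2 already uses these categories for the baseline ECG, and footnote 2 asks for them at each examination.

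The cost is a protocol clarification, a site memo, one SAP sentence and one or two descriptive tables. The downside of the first change is that NCS findings leave the AE tables. The third change keeps them visible.
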